For the control group, this protocol includes 24 one-hour sessions of cRHB training during 8 weeks three times per week, under the supervision of a qualified rehab team.

For the intervention group (RAGT) this protocol includes 24 one-hour sessions of RAGT during 8 weeks three times per week, under the supervision of a qualified rehab team.

Additionally, peripheral blood (6ml) will be taken from all subjects at three timepoints: at baseline (T1), after the 8 weeks of rehabilitation treatment (T2) and, if possible, one year after T4. Biological samples will then be given a unique identifier and transferred to researchers for analysis.

Informed consent will be obtained from patients prior to inclusion in the study, which will be carried out in accordance with the Declaration of Helsinki.

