3.6 Intervention

The intervention will be delivered through the Neurorehabilitation Cemcat team.

Traditional Gait Rehabilitation training (tRHB):

Participants randomize to receive a tRHB, will be trained 3 times per week, with an intensity of 40 to 60 minutes, and duration over 8-weeks. Progression will occur by increasing the session intensity weekly.

A standardized protocol based on the usual clinical practice of physiotherapy in people with multiple sclerosis will be follow, according to patient characteristics, to design the sessions based on the patient objectives to be achieved, choosing the type of specific exercises to be performed based on the patient's condition and with the possibility of adapting them to their evolution during the twenty-four sessions.

PHYSIOTHERAPY TREATMENT PROTOCOL			
Goal	To re-educate the balance (sitting and standing).	To normalize upper limbs muscle tone	To improve the upper limbs muscular balance (MB)
Intervention	Trunk work on stable surface: anterior-flexion, lateralization and turns to make appear the straightening reactions (5 minutes)	Local cryotherapy application to the most affected muscles using cold-packs (15 minutes)	If BM = 1: isometrical exercises of deltoid, bicep, triceps, carpal extensors and carpal flexors (3 sets of 5 repetitions for each muscular group)
	Trunk work on instable surface (air cushion): anterior flexion, lateralization and turns to make appear the straightening reactions (5 minutes)	Inhibitory postural treatment in flexion, abduction and external rotation of humeral-scapula for the flexor patterns during cryotherapy application	If MB = 2: Weight-bearing and/or active-assisted exercises for deltoids, biceps, triceps, carpal extensors and carpal flexors (3 sets of 5 repetitions for each muscle group)
	Balance work with Bobath ball (5 minutes)	Passive mobilizations and myotendinous stretching of spastic musculature (5 minutes)	If MB= 3 : active-resisted exercises with $\frac{1}{2}$ kg of deltoid, bicep, triceps, carpal extensors and carpal flexors (3 sets of 5 repetitions for each muscular group)
	Balance standing exercises at bars: antero-posterior and lateral load transfer, different support bases, and changing props and surfaces (10 minutes)	Pectoral and brachial biceps kneading and lats stretching (5 minutes)	If MB = 4: active-resisted exercises with 1 kg of deltoid, bicep, triceps, carpal extensors and carpal flexors (3 sets of 5 repetitions for each muscular group)

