	Running treadmill with speed and inclination according to tolerance (2-6 minutes)	Passive verticalization at standing or inclined plain to reduce the flexor musculature hypertonia (10 minutes)	If MB = 5: active-resisted exercises with 2 kg of major glutes, psoas, quadriceps, hamstrings and anterior tibial (3 sets of 5 repetitions for each muscular group)
	Weight-bearing walking (5 minutes).	Active verticalization at the shoulders or parallel bars in order to reduce the hypertonia of the flexor muscle (5-10 minutes)	Step from sitting to standing (3 sets of 5 repetitions)
	Vibratory stimulation in bilateral plantar zone (5 minutes)	Antero-posterior and lateral pelvic tilting exercises to encourage straightening reactions and reduce upper limbs hypertonia. (5-10 minutes)	Go up and down 20 stair's steps
		Pelvic and trunk rotations to decrease trunk extension hypertonia (5 minutes)	Active-resisted cycloergotherapy, resistance according to symmetry (10 minutes)
		Passive cycle ergotherapy adapting speed to tolerance and avoiding spasms during exercises (10 minutes).	

Atalante Gait training (RAGT):

Participants randomize to receive a Atalante gait training, will be trained 3-times per week, with an intensity of 40 to 60 minutes, and duration over 8-weeks. Progression will occur by increasing the session intensity weekly. Training intensity will be monitored and standardized using the Borg Rating of Perceived Exertion scale, and will progress from 'fairly light' to 'somewhat hard'. This prescription is consistent and appropriate for individuals with MS with mobility impairment and low fitness levels. Progression will occur by increasing the intensity of the session increase the number of steps in each session and decrease the level of assistance. Sessions will not exceed 60 minutes. We will record all training parameters.

Using the Atalante System, participants will be secured with the appropriately sized harness and attached to an overhead body-weight support system. Each session will begin with a 3–5-minute warm-up in the continuous passive mode (cadence ~40-45 steps/minute). The participant will then be transitioned into the adaptive training phase for practicing repetitive floor walking for up to 30 minutes. During this phase, the force produced by the robot is modulated to support the effort of the patient in producing a typical walking pattern.

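### Borg exertion is listed under a between-arm aim but scheduled only under the robot-session column of Table 1; as a minor point, the stated RAGT session lengths need reconciling

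*Combined protocol and SAP*

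**What the plan says.** **Borg.** Section 2.2 (Secondary Aims) has an aim comparing RAGT with cRHB on quality of life, emotional status and fatigue. One item under it is perceived effort on the Borg scale, rated when each training session ends, with no restriction to one arm. Table 1 (section 3.4) gives Borg a single mark, in the block of columns labelled for RAG sessions 1 to 24. That is the only per-session block in the table. In section 3.6 the RAGT text uses Borg to monitor and standardise training intensity. The control text (there called tRHB) says that intensity rises weekly but names no measure of it.

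**Duration.** Section 3.1 states "For the control group, this protocol includes 24 one-hour sessions of cRHB training" and, for the other arm, "For the intervention group (RAGT) this protocol includes 24 one-hour sessions of RAGT during 8 weeks three times per week". Section 3.6 says that control participants "will be trained 3 times per week, with an intensity of 40 to 60 minutes, and duration over 8-weeks" and that RAGT participants "will be trained 3-times per week, with an intensity of 40 to 60 minutes, and duration over 8-weeks", adding for RAGT "Sessions will not exceed 60 minutes". The RAGT weekly table, in a row headed by session number and time, gives 40 min for session 1, 30 min for sessions 2 and 3, 30–35 min in week 2, 35–40 min in week 3, and 40 min in weeks 4 to 8.

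**The concern.** A between-arm aim needs the measure in both arms. If staff follow Table 1 as labelled, effort is rated after robot sessions only, and the comparison promised in section 2.2 has no control data. A rating taken at the end of a session cannot be reconstructed afterwards, so the gap would be permanent.

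The duration texts raise a smaller question. Someone delivering an early RAGT session cannot tell from the protocol whether it should last 30 minutes, at least 40, or an hour. Recording of training parameters is stated only for RAGT, and nothing says that session minutes are recorded for controls. As written, exposure might not be reportable by arm.

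**Working it through.** **Borg: the passages side by side**

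| Place | Who is rated | When |
|---|---|---|
| Section 2.2 | both arms, by the wording of the parent aim | end of each training session |
| Table 1 | RAG sessions, by the column label | sessions 1–24; no mark at T1 to T4 |
| Section 3.6, RAGT text | RAGT | during training, to steer intensity |
| Section 3.6, control text | not mentioned | – |

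The other items in the same Table 1 block do not settle whether the label is literal:
- Heart rate and blood pressure are marked there, and section 3.4 assesses them weekly in patients generally. This suggests a loose label.
- The pain registry and the spasticity rating are marked there too, and section 3.4 ties both to RAGT. This suggests a literal one.

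Count on the literal reading: 3 sessions × 8 weeks = 24 ratings per RAGT participant, so up to 24 × 30 = 720 in that arm and none explicitly scheduled in the control arm. Covering controls adds at most 24 × 30 = 720.

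**Duration: the stated figure against the weekly table**

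The session count reproduces: 3 × 8 = 24. The length does not follow from the table:
- Lower total: 40 + 2×30 + 3×30 + 3×35 + 15×40 = 895 min, or 895/24 = 37.3 per session.
- Upper total: 40 + 2×30 + 3×35 + 3×40 + 15×40 = 925 min, or 925/24 = 38.5 per session.
- Sessions below 40 min: 2 (sessions 2 and 3) + 3 (week 2) = 5. Week 3 may add 3, giving 8. The other 16 are at 40, and none is longer.
- Against 24 sessions at the 40-min floor (24 × 40 = 960): short by 960 − 925 = 35 to 960 − 895 = 65 min in total, or about 1.5 to 2.7 min per session.

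These shortfalls apply only if the table gives full session time. Three checks bear on that:
- *Timed activities.* Week 2: 10+5+5+5+5 = 30 min (header 30–35). Week 3: 5+5+5+5+5+10 = 35 min (header 35–40). Week 4: 5+5+5+5+5+10 = 35 min (header 40). Weeks 5 to 8 also come to 35 min each if the four cells of the broken last row belong to those weeks, which is an inference. Squat series are untimed throughout.
- *Warm-up.* Section 3.6 says "Each session will begin with a 3–5-minute warm-up in the continuous passive mode", but the table has no warm-up line. If it is extra, the total is 895 + 24×3 = 967 to 925 + 24×5 = 1,045 min, above 960. Sessions 2 and 3 would still be 33–35 min.
- *Walking phase.* Section 3.6 describes "practicing repetitive floor walking for up to 30 minutes". With the warm-up that is at most 33–35 min, so the prose itself leaves part of a 40-to-60-minute session to other things.

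**The case against.** On Borg, the best reply is that the column label is a slip. Section 2.2 says which arms are compared and when the rating is taken, Table 1 offers only one place for a per-session item, and heart rate and blood pressure sit there although they are not confined to RAGT. This is a fair reading, and it stands to this extent: a reader might infer that control ratings will not be collected, and the documents do not establish that. It does not remove the problem. Two other items in the column are tied to RAGT, and the only operational use of Borg in section 3.6 is to steer RAGT intensity. Site staff could reasonably follow the label.

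On duration, the case for exercise time only is strong. The timed items nearly fill the headers before squats or warm-up are counted. Sections 3.4, 3.5.1 and 3.6 describe fitting, transfer, harness attachment and a spasticity rating before each RAGT session, and the table lists none of these as recurring items. Pointing the other way, the row is headed as session time, and session 1 includes taking the patient's measurements. The documents give no set-up minutes, so the question stays open, with the balance towards exercise time.

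A reader might also infer that RAGT participants are planned less training than controls and that this biases the walking-speed comparison. The documents do not support that. Sections 3.1 and 3.6 each give both arms the same length, and one hour is simply the top of the 40-to-60 range. Setting table minutes against a full hour would pair the shortest reading of one arm with the longest of the other. Even a real difference in time would limit attribution to the device rather than bias the comparison of the two packages.

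**Conclusion.** The Borg point holds. As written, a stated between-arm comparison has no explicitly scheduled control data: up to 24 ratings per RAGT participant against none. Loss of that comparison is a risk that depends on staff following the column label literally; it is not a certainty. It touches one secondary measure and leaves the 10-MWT primary endpoint alone. It is worth correcting because the remedy is almost free and missed ratings are irrecoverable.

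The duration point is minor. The weekly table does not match the lengths in sections 3.1 and 3.6 on its face, with 5 to 8 of 24 sessions below 40 min, but it may not be measuring the same thing. What is established is that the table's minutes are undefined. Unequal planned time between arms is not.

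**What to change.** 1. **Borg.** Relabel the Table 1 session column so that Borg is scheduled at training sessions in both arms, and name it in the control text of section 3.6. If Borg is meant only to monitor RAGT, remove it from the between-arm aim in section 2.2 instead. The first option costs at most 720 one-number ratings, taken by staff already present; the second costs a line of text.
2. **Duration.** Reconcile section 3.1, both arm descriptions in section 3.6 and the RAGT weekly table, and state whether the table's minutes include warm-up, fitting, transfer and set-up. The investigators decide which figure stands. This is wording only.
3. **Exposure.** Record actual session minutes in both arms and report them by arm. This adds one short entry per control session, which can share a form with the Borg rating if that is kept.

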3.2 Inclusion and exclusion Criteria

Subjects will be evaluated for their eligibility from neurorehabilitation and neurology outpatient clinics at the Multiple Sclerosis Center of Catalonia (Cemcat).

3.2.1 Inclusion criteria

- Male or female, between 18 and 75 years of age.
- Confirmed diagnosis of MS.
- EDSS from 6.0 to 7.0.
- Able to maintain the upright position on a daily basis.
- Stable course of disease-modifying therapy over the past 6 months.
- Clinical comorbidity asymptomatic (i.e., no underlying cardiovascular disease)
- Height: between approximately 1.50 m. and 1.90 m.
- Willingness to visit the Multiple Sclerosis Center of Catalonia (Cemcat) for testing and training.
- Gait disorder conditioned by paresis or hemiparesis associated with ataxia or sensory problems.
- Patient having given written consent.
Atalante is able to accommodate the following limb lengths:
- Thigh: 380-460mm.
- Distance between the ground and the joint space of the knee (to be measured while wearing the shoes they intend to wear with Atalante):
 - 457–607mm for patient with an ankle dorsiflexion $\geq 16^\circ$
 - 457–577mm for patient with an ankle dorsiflexion between 13° et 16°
 - 457–567mm for patient with an ankle dorsiflexion between 10° et 13°
 - 457–557mm for patient with an ankle dorsiflexion between 0° and 10°
- Hip with less or equal to 460mm when seated.
- Maximum weight: 90 kg.

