comes in a clinically meaningful way in PwMS, RAGT seems more effective compared to conventional rehabilitation, while it shows similar effects if compared to specific balance and gait training in studies with level 2 evidence.¹¹ RAGT has several advantages in terms of patient motor assistance, intensity of training, safety, and the possibility to combine other therapeutic approaches and should be promoted for PwMS with severe disability in a multimodal rehabilitation context as an opportunity to maximize recovery.¹¹ In this context is needed a further larger-scale, better-designed RCTs with a longer training duration and more studies evaluating the satisfaction, usability and effectivity of RAGT.^{10 12 13 11}

The Atalante exoskeleton is composed of an external, powered, motorized orthosis that is placed over a person's limbs to provide self-ambulation functions without the use of crutches or other technical aids. The main feature of the exoskeleton is that it is fully actuated with 12 actuated degrees of freedom: three at each hip, one at each knee, and two at each ankle.^{14 15}

The molecular bases associated with the functional improvements derived from rehabilitation therapies or physical exercise are not yet well defined. However, both rehabilitation and exercise have been recognized for their immunomodulatory properties. In fact, recent clinical and preclinical findings have established a connection between physical activity and rehabilitative interventions with discernible epigenetic alterations in immune cells. For example, recent preclinical research has demonstrated how moderate-intensity training induces lasting changes in chromatin accessibility in macrophages, resulting in moderation of their inflammatory responses. However, there is still a lack of comprehensive epigenomic studies examining the repercussions of rehabilitation therapies in individuals with multiple sclerosis.

2 Aims

2.1 Primary Aim:

- To compare the effect of RAGT by use of Atalante self-balance exoskeleton with conventional rehabilitation training (cRHB) for improving **Walking speed** measured by the Timed 10-meters walk test (10-MWT), considering a clinically relevant change an improvement of 20% of the velocity (m/s) with respect to the baseline assessment.¹⁶

2.2 Secondary Aims:

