3.3 Enrollment and Screening

Subjects will be evaluated for their eligibility from neurorehabilitation and neurology outpatient clinics at the Multiple Sclerosis Center of Catalonia (Cemcat).

Potential subjects will be referred to the study via Cemcat Physicians. A member of the research team will screen the referral and confirm they meet the necessary inclusion and exclusion criteria. Following confirmation of criteria, potential subjects will be contacted by phone to schedule an initial visit for consent and baseline assessment.

Additionally, peripheral blood (6ml) will also be taken from all subjects at baseline (T1).

Prior to all testing, each of the 60 selected participants will have time to read the consent form and ask questions (see Draft Informed Consent). The consent process will take place at the Multiple Sclerosis Centre of Catalonia (Cemcat, Vall d'Hebron Barcelona Hospital Campus, [name]).

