3.4 Assessments

The following information will be collected for all patients: age, sex, weight, height, type of MS, years from the diagnosis, Expanded Disability Status Scale (EDSS) and type of support device.

To ensure that training sessions are well tolerated, we will assess patients' blood pressure and heart rate weekly. We will also monitor the appearance of pain in any part of the body related to the RAGT at end of each training session using a pain registry (type of pain, location, intensity)²⁷.

3.4.1.1 To reduce the incidence of any type of muscle injury the physical therapist before each RAGT session will assess the level of spasticity using the Numeric Rating Scale measure of spasticity (NRS). The 0–10 NRS asks patients to indicate their level of spasticity on a scale of 0–10, where 0 is no spasticity and 10 is the worst possible spasticity. This type of rating tool is widely utilized in clinical settings to quickly assess pain.²⁸

A record of any unexpected Serious Adverse Events (SAE) within trial episodes will be kept. These are defined as death, a life-threatening adverse event or an event occurring as a result of the use of the device that requires medical intervention.

After the 8 weeks of rehabilitation treatment (T2) and, if possible, one year after T4, peripheral blood (6ml) will be taken from all subjects to perform the subsequent molecular analysis.

Molecular analysis

Peripheral blood mononuclear cells (PBMCs) will be purified using the Ficoll-Hypaque density gradient method according to manufacturer's instructions. Briefly, whole blood will be extracted by venepuncture and collected in CPT Vacutainer tubes (Becton Dickinson, BDAM362781) and centrifuged at 2250g for 25 min. Supernatant will then be collected, and washed twice with enriched saline (0.9% NaCl, 2%FBS). PMBC containing pellet will then be resuspended with 1 ml of complete media (RPMI1640 + 2% FBS) and cells will be counted and assessed for viability using a Countess 3 automated cell counter (Invitrogen). PBMCs will be adjusted to 5×10^6 cells/ml in freezing media media (90% FBS, 10% DMSO), and frozen at -80°C using a [name]™ Freezing Container (Thermo Scientific™) for 24 h and stored in liquid nitrogen vapor phase.

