Descriptive statistics (i.e., mean, standard deviation) will be calculated for quantitative data (demographics and clinical characteristics and outcome measures). Frequencies will be calculated for qualitative variables. For the proportions, binomial proportion confidences will be calculated using the Wilson formulae. Proportions will be compared using the Newcombe formulae

The Wilcoxon bilateral matched-pairs test will be used to compare repeated measurement on a single sample (mean, standard deviation).

Study data were collected and managed using REDCap electronic data capture tools hosted at the Mayo Clinic. REDCap (Research Electronic Data Capture) is a secure, web-based application designed to data capture for research studies, providing: 1) an intuitive interface for validated data entry; 2) audit trails for tracking data manipulation and export procedures; 3) automated export procedures for seamless data downloads to common statistical packages; and 4) procedures for importing data from external sources (Harris et al., 2009).

5 References

6. Larocca NG. Impact of Walking Impairment in Multiple Sclerosis Perspectives of Patients and Care Partners Conclusions: Difficulty walking is a common impairment in people with MS, with adverse effects on the QOL of people with MS and care partners of a person with MS. *Patient.* 2011;4(3):189-201.

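### No criterion secures a completed 10-metre walk at baseline, and no rule scores a patient who cannot complete the test at T1 or T2, so the 20% gain can be undefined or missing

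*Combined protocol and SAP*

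**What the plan says.** The primary aim (section 2.1) is to compare the two arms on walking speed by the 10-MWT, "considering a clinically relevant change an improvement of 20% of the velocity (m/s) with respect to the baseline assessment".

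Three inclusion criteria in section 3.2.1 bear on function: "EDSS from 6.0 to 7.0", "Able to maintain the upright position on a daily basis", and "Gait disorder conditioned by paresis or hemiparesis associated with ataxia or sensory problems". Neither the inclusion nor the exclusion list asks for a completed 10-MWT, a walking distance or a minimum speed.

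Section 3.3 puts the eligibility check ahead of the baseline test: "Following confirmation of criteria, potential subjects will be contacted by phone to schedule an initial visit for consent and baseline assessment". Section 3.4 records "Expanded Disability Status Scale (EDSS) and type of support device" but does not say whether an aid is used in the 10-MWT.

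Section 4 gives descriptive statistics, Wilson intervals, a matched-pairs Wilcoxon test for repeated measurements on a single sample, and for proportions "Proportions will be compared using the Newcombe formulae". It has no rule for an uncompleted test and no baseline-adjusted comparison of speed between arms.

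**The concern.** A percentage gain over baseline needs a baseline speed above zero and a speed at T2. The plan secures neither and does not say what happens when one is absent. The value is then missing because of the very function being measured.

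The two gaps have different consequences. Inability at T1 is a characteristic present before the intervention. Leaving such patients out of both arms alike shrinks the sample and narrows the population to which the result applies, but does not in itself bias the arm comparison. Inability at T2 arises after randomisation and may depend on treatment. Dropping those patients removes the worst outcomes and could bias the comparison.

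Without a written rule, the choice between excluding these patients, counting them as failures or counting them as successes would be made after the data are seen. With 60 patients, a few such choices could matter.

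A second, conditional worry is that at very low baseline speeds a 20% gain is a very small absolute change.

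**Working it through.** **The plan's own figure.** Section 4 states 15 patients from a 70% success rate, two-sided 5% alpha and 80% power, with no null or comparator rate. It cannot be reproduced without supplying one. As a two-arm comparison, 15 per arm follows if the comparator rate is 20%. As a single-arm normal approximation, the result is 14.2 for a null of 35% and 15.2 for 36%. The 35% comparator used below is therefore an assumption.

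**Step 1: when the change is defined.** Let v1 and v2 be the speeds at T1 and T2. Change = (v2 − v1)/v1.
- Completes both tests: defined.
- Unable at T1, completes at T2: undefined (division by zero, or no v1).
- Unable at both: undefined.
- Completes at T1, unable at T2: no v2. A score of 0 would give −100%, but the plan assigns no score.

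This step needs no outside figure.

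**Step 2: illustrative cost in power.** From the documents: 30 per arm (section 3.1), 70% success (section 4, taken from a spinal cord injury study), two-sided 5%. Assumed: 35% in the comparator arm and 20% non-walkers in each arm.
- Excluded: 30 × 0.8 = 24 per arm, 70% versus 35%.
- Counted as failures: 0.70 × 0.8 = 56% versus 0.35 × 0.8 = 28%, with 30 per arm.

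Power was found by enumerating all outcomes and checking whether the 95% Newcombe interval excludes zero. The check is a normal approximation, Φ[(|p1 − p2| − 1.96·se0)/se1], where se0 is pooled and se1 unpooled. For 30 per arm it is (0.35 − 1.96 × 0.1289)/0.1208 = 0.81, giving 79%.

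| Handling | Newcombe, exact | Normal approximation |
|---|---|---|
| No non-walkers | 79.8% | 79.0% |
| 20% excluded | 72.5% | 69.1% |
| 20% counted as failures | 60.4% | 59.8% |

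By the normal approximation, 10% and 30% non-walkers give 74% and 63% if excluded, and 70% and 50% if counted as failures. At 20%, the handling choice alone moves exact power by 72.5 − 60.4 = about 12 points.

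**Step 3: the threshold at low speed.** The threshold is 0.2 × v1: 0.02 m/s at 0.1 m/s (100 s falling to 83.3 s), 0.04 m/s at 0.2 m/s (50 s to 41.7 s) and 0.10 m/s at 0.5 m/s (20 s to 16.7 s).

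The documents give no test error. If each test has an SD s that is constant in m/s, an unchanged patient appears to gain 20% with probability 1 − Φ[0.2·v1/(s√2)]. For v1 = 0.1 and s = 0.05: 0.02/0.0707 = 0.283, giving 39%.

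| Assumed s (m/s) | v1 = 0.1 | v1 = 0.2 | v1 = 0.5 |
|---|---|---|---|
| 0.02 | 24% | 8% | 0% |
| 0.03 | 32% | 17% | 1% |
| 0.05 | 39% | 29% | 8% |
| 0.07 | 42% | 34% | 16% |

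If error is instead proportional to speed, say s = 0.1 × v1, then v1 cancels: 0.2/(0.1 × √2) = 1.41, or about 8% at every speed.

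**The case against.** **Entry is not based on standing alone.** A reader might infer that anyone able to stand can enrol and that non-walkers will. The documents do not support that. EDSS 6.0 to 7.0 and a gait disorder are also required, and the type of support device is recorded. What stands is narrower: the documents translate none of these into a walking distance, so non-walkers are not expressly excluded and their number is unknown.

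**The primary analysis may not be a percentage.** Section 2.1 names speed as the measure and 20% as the relevant change. Section 4 never says whether m/s, percentage change or the responder proportion is primary. The success-rate sample size and the Wilson and Newcombe methods point to responders, but that is an inference. If m/s is primary, the low-speed instability goes away; patients unable to complete the test would still have no value.

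**Bias does not run in both directions.** It is tempting to call both gaps informative missingness. Section 3.4.2 puts the day 1 assessments before the intervention, so exclusion for baseline inability, applied equally to both arms, costs power rather than validity. Only loss of walking by T2 carries the risk of bias.

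**The noise figures are weak where they look worst.** At 0.1 m/s, an SD of 0.05 is half the value measured, and a normal model would put about 2% of measured speeds below zero (about 8% for SD 0.07). Under proportional error the gradient disappears. That the responder label is mostly noise in slow walkers is not established.

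**The power figures are hypothetical.** The comparator rate and the non-walker share are assumed, and exact power is uneven in sample size (73.5% at 27 per arm, 72.5% at 24). They show the order of magnitude of a handling choice and are not a forecast.

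**Conclusion.** The point holds in a limited form. The plan does not secure a baseline 10-MWT speed, its 20% criterion is undefined without one, and nothing in section 4 scores a patient who cannot complete the test at T1 or T2. That much rests on the text and on algebra.

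The size is unknown because the share of such patients is not given. Under the stated assumptions, 20% non-walkers would lower power from about 80% to 73% or 60%, depending on a rule the plan does not contain. The possible bias comes from loss of walking after randomisation and is not quantified here. Frequent false responses at 0.1 to 0.2 m/s are possible if test error is roughly constant in m/s, and do not follow if error is proportional to speed.

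The documents do not show that non-walkers will be enrolled, or that the primary result would be biased by baseline inability. The gap should still be closed before outcome data are seen, because the repair is cheap and uses data already collected.

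**What to change.** In section 4:
- Score velocity as 0 m/s at any visit where the patient cannot complete the 10-MWT with the usual aid.
- Make the primary between-arm comparison T2 velocity in m/s, adjusted for baseline velocity.
- Keep the 20% responder rate as supportive. Count loss of walking and 0 at both visits as non-response, and state before outcome data are seen how a change from 0 to walking is counted.

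The cost is a short addition to section 4: the scoring rule, the responder rules and a baseline-adjusted model that the plan now lacks. No new measurement is needed.

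An alternative for T1 only is to require a completed baseline 10-MWT for entry. This slightly narrows recruitment and still needs the T2 scoring rule.

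Neither option supplies T2 data for patients removed under the rule in section 3.4.2 on three consecutive missed sessions, so neither guarantees a value for all 60 patients.
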